In order to acquire baseline data, standard MRI will be performed before intervention, if not already done during diagnosis by an external radiology department. The patient will be given the relevant questionnaires in order to collect the baseline data for the clinical scores and assigned to a treatment group by randomization.

3-5 weeks before the surgery, depending on the treatment group, a nasal cartilage biopsy and autologous blood (72ml), needed for the manufacturing, are harvested under local anesthesia. After 3-5 weeks of manufacturing the graft or cell-seeded scaffold is implanted.

Clinical follow-up will be done at 6 weeks as well as at 3, 12 and 24 months to assess recovery. After 3, 12 and 24 months an MRI will be performed in addition to the clinical assessment, and questionnaires filled out by the patient (12 und 24 months) to collect the clinical data.

Study Product / Intervention:

The active components of the tissue engineered cartilage graft (N-TEC) are expanded human autologous nasal chondrocytes and cartilage matrix proteins produced by the cells. The N-TEC is generated using autologous nasal chondrocytes isolated by enzymatic digestion from a 6mm diameter biopsy of the nasal septum and expanded for 2 weeks in monolayer. After expansion, 50 million cells are seeded on a 30 x 40 mm collagen membrane (Chondro-Gide®) and cultured for two additional weeks to allow for extracellular matrix deposition by the cells. The graft is cut and shaped by the surgeons according to the defect size and implanted in the knee using suturing. The graft is expected to heal in the defect and integrate with the adjacent tissue.

Document:	Clinical Study Protocol
Version:	V07
Page number:	14 of 80
Acronym	Nose to Knee II

Secondary treatment arm:	The active component for the cell-seeded scaffold (N-CAM) is expanded human autologous nasal chondrocytes. The product for the secondary treatment arm is generated in the same way as the study product, but only cultured for 2 days after cell seeding onto the scaffold. Therefore the cells are attached to the scaffold, but no extracellular matrix produced. The graft is cut and shaped by the surgeons according to the defect size and implanted in the knee using suturing. The graft is expected to heal in the defect and integrate with the adjacent tissue.

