	Failure to generate a graft	medium	if the standard surgical method has to be used, there is no disadvantage	acceptable	
	Cell number for seeding not reached	medium	 working according to SOPs correct biopsy size 	minor	In case of <50M and >38M cells, ≥95% viability and adequate morphology seeding of a smaller scaffold
	contamination with	the construct is a critical risk. Since most cultures show signs in 48h, the sample of the last media change is taken 48 - 72h prior ast result will be retrospective regarding microbiological contamination.		18 - 72h prior to	
Risk		Initial risk	Risk Control/Mitigation	Residual Risk	Contingency Plan
itient	Infection during surgical intervention at the biopsy site	minor	 standard preparation of patient for operation additional treatment of the biopsy site to avoid infection routine precautions as in any operation 	acceptable	
Safety for patient	Infection through transplant	minor	no positive tests regarding mycoplasma, endotoxin or microbiological contamination (last result retrospective)	acceptable	
	Infection after operation	minor	same as for standard operation	acceptable	

Document:	Clinical Study Protocol
Version:	V07
Page number:	45 of 80
Acronym	Nose to Knee II

			close follow up of patient		
	Complications after implantation	minor	 same as for standard operation arthroscopy to determine cause and further treatment 	acceptable	
	Loss of implant	minor	same as for standard operation	acceptable	
	Rejections and immune reaction	minor	autologous cells and serum are used	acceptable	
	Contrast agent (Dotarem®)associ ated with nephrogenic systemic fibrosis	minor	exclusion of patients with renal impairment	acceptable	
	Allergic or hypersensitive reactions to contrast agent (Dotarem®)	minor	 patients with known allergies or asthma will receive anti-allergy medication before operation 	acceptable	
	Allergic reaction to antibiotics used partially during production	minor	exclusion of patients with known allergies	acceptable	
	Unforeseen side effects	minor	 immediate contact with study doctor for further investigation and treatment 	acceptable	
Risk		Initial risk	Risk Control/Mitigation	Residual Risk	Contingency Plan
	Insufficient patient information	minor	no participation of patient without signed informed consents	acceptable	

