5.2 Secondary Outcomes

The stability and integration as well as the morphological properties of the graft will be assessed by the MOCART and 3D MOCART Scores (magnetic resonance observation of cartilage repair tissue) derived from the MRI. The secondary endpoint will be the 24-month assessment. MRI will be performed at 3, 12, 24 months follow-up.

The remodeling of the tissue after implantation towards native cartilage will be assessed by dGEMRIC evaluation (MRI) from the 24-month assessment of the relative \Box R1. The dGEMRIC evaluation will be recorded at 3, 12, 24 months follow-up.

The KOOS will be recorded for patients at baseline visit 1 or 2 and at the 12- and 24-month follow-up assessments. Variations over time will be recorded through completion of the questionnaires at enrolment and at each follow-up visit (12 and 24 months after treatment). An increase of at least 10 points after 2 years in the KOOS is considered a relevant improvement for the patient, thus proving the efficacy of the treatment.

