- The patient has at the site of surgery an active systemic or local microbial infection, eczematization or inflammable skin alterations (including Protozoonosis: Babesiosis, Trypanosomiasis (e.g. Chagas-Disease), Leishmaniasis, persistent bacterial infections, such as Brucellosis, spotted and typhus fever, other Rickettsiosis, Leprosy, Recurrent Fever, Melioidosis or Tularaemia).
- Patient has a known history of cancer.
- Patient has a known history of primary hyperparathyroidism, hyperthyroidism, reduced kidney function (GFR < 80 ml/min), or prior pathological fractures, independent of the genesis.
- Patient has any degenerative muscular, vascular or neurological condition that would interfere
 with evaluation of outcome measures including but not limited to Parkinson's disease,
 amyotrophic lateral sclerosis (ALS), or multiple sclerosis (MS).
- Patient has a body mass index (BMI) >35 kg/m².
- Patient is pregnant, lactating or anticipates becoming pregnant within 24 months after surgery.
- Patient is currently participating, or has participated in any other clinical study within 3 months
 prior to the screening visit.
- Patient has known current or recent history of illicit drug or alcohol abuse or dependence defined as the continued use of alcohol or drugs despite the development of social, legal or health problems.
- Patient has psychiatric or cognitive impairment that, in the opinion of the investigator, would interfere with the patient's ability to comply with the study requirements, e.g., Alzheimer's disease
- Patient has any other condition, which, in the opinion of the investigator, would make the patient unsuitable for the study.
- · Patient is unable to tolerate local anesthesia
- Any known allergies, especially for porcine collagen, penicillin or streptomycin
- Patient is unwilling and/or unable to give written informed consent to participate in the study and to comply with all study requirements, including attending all follow-up visits and assessments and to complete postoperative rehabilitation regimen.

Intraoperative Exclusion Criteria:

- Patient has a total defect size <2 or defect size extends graft size and could therefore not be treated in total.
- Patient has >2 independent cartilage lesions
- Patient has symptomatic full-thickness (ICRS Grade 3 or 4) of tibial plateau.

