8.6 Trial specific preventive measures

There are no specific preventive measures for this trial apart from the ones taken for standard operations. Pregnancy tests will be performed at time of enrolment. Contraception using a reliable method such as hormonal in combination with a mechanical contraception or double mechanical contraception such as diaphragm in combination with condom is advised during study participation.

Immunosuppressive medication is not allowed during study participation, as it could increase infection rate and/or mask signs of inflammation/infection.

Steroidal medication is not allowed during study participation as it could compromise repair tissue formation.

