9.3 Procedures at each visit

9.3.1 Visit 1: Screening visit (-240 days or less)

The screening visit will take place after the informed consent has been signed. Blood will be taken from the patient and sent to the respective laboratories for analysis of the parameters listed in the inclusion and exclusion criteria. MRI can be performed if not available from a recent visit to an external physician. Questionnaires will be filled to see, if the patient fulfills inclusion and exclusion criteria. The visit should take place maximal 8 months before the treatment start (Biopsy harvesting). If all inclusion and exclusion criteria are met, the patient can be randomized.

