9.3.6 Visit 6: Clinical follow-up and efficacy assessment (Day 90 (3m))

The wound healing will be checked and the patient asked about any AEs. In addition the patient will be asked about any consequences from the harvesting procedure of the nasal cartilage and the ongoing or completed physiotherapy. Furthermore an MRI/dGEMRIC will be performed to assess the stability

Document:	Clinical Study Protocol
Version:	V07
Page number:	59 of 80
Acronym	Nose to Knee II

and remodeling of the graft. The renal function will be assessed before the contrast agent (Dotarem[®]) is given.

9.3.7 Visit 7-8: Clinical follow-up and efficacy assessment (Day 360 (12m), Day 720 (24m))

The wound healing will be checked and the patient asked about any AEs. In addition the patient will be asked about any consequences from the harvesting procedure of the nasal cartilage and the ongoing or completed physiotherapy. Furthermore the patient will be asked to fill out the questionnaires regarding the clinical scores (KOOS, EQ-5d) and an MRI/dGEMRIC will be performed to assess the stability and remodeling of the graft. The renal function will be assessed before the contrast agent (Dotarem [®]) is given.

Document:	Clinical Study Protocol
Version:	V07
Page number:	60 of 80
Acronym	Nose to Knee II

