10.1.2 Reporting of serious adverse events (SAE) and other safety related events

Reporting of SAEs

All SAEs must be reported immediately and within a maximum of 24 hours to the Sponsor-Investigator of the study or his substitute. The Sponsor-Investigator will re-evaluate the SAE.

SAEs resulting in death are reported to the local Ethics Committee (via local Investigator) within 7 days.

The other Ethics Committees involved in the trial as well as Swissmedic receive SAEs resulting in death via Sponsor-Investigator within 7 days.

Reporting of SUSARs

A SUSAR needs to be reported to the local Ethics Committee (local event via local Investigator) and to Swissmedic for category B and C studies (via Sponsor-Investigator) within 7 days, if the event is fatal, or within 15 days (all other events).

The Sponsor-Investigator must inform all Investigators participating in the clinical study of the occurrence of a SUSAR. All Ethics Committees involved in the trial will be informed about SUSARs in Switzerland via Sponsor-Investigator according to the same timelines.

All SAEs having a suspected link to the IMP administered (Serious adverse drug reaction (SADR)) must be reported in the same way as SUSARs.

Reporting of Safety Signals

All suspected new risks and relevant new aspects of known adverse reactions that require safety-related measures, i.e. so called safety signals, must be reported to the Sponsor-Investigator within 24 hours. The Sponsor-Investigator must report the safety signals within 7 days to the local Ethics Committee (local event via local Investigator) and to Swissmedic in case of a category B or C study.

The Sponsor-Investigator must immediately inform all participating Investigators about all safety signals. The other Ethics Committees involved in the trial will be informed about safety signals via the Sponsor-Investigator.

Reporting and Handling of Pregnancies

Pregnant participants will be followed-up in the normal way, but will not be subjected to the dGEMRIC MRI due to the need to apply a contrast agent (Dotarem®). Further follow-up after the end of the study and the outcome of the pregnancy is not necessary.

Periodic reporting of safety

A development safety update report (DSUR) is submitted once a year to the local Ethics Committees and to the national authorities via Sponsor-Investigator.

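### Two contrast-agent safeguards, the allergy medication and the pregnancy test, do not match the visits at which contrast is given

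*Protocol*

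**What the plan says.** **Where contrast is given.** Protocol section 5.2: "The dGEMRIC evaluation will be recorded at 3, 12, 24 months follow-up". Sections 9.3.6 and 9.3.7 place the combined MRI/dGEMRIC at Visits 6, 7 and 8, with Dotarem. For the baseline scan, the synopsis (measurements and procedures) says: "In order to acquire baseline data, standard MRI will be performed before intervention". Section 9.3.2 likewise asks for an MRI without naming dGEMRIC. The implantation visit (9.3.4) mentions no contrast.

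**Allergy.** The Table 3.7.1 row on allergic or hypersensitive reactions to Dotarem has a single mitigation: "patients with known allergies or asthma will receive anti-allergy medication before operation". The residual risk is rated acceptable. Section 7.1 excludes patients sensitive to gadolinium, and separately: "Any known allergies, especially for porcine collagen, penicillin or streptomycin".

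**Pregnancy.** Section 8.6: "Pregnancy tests will be performed at time of enrolment". The schedule in 9.1 has one mark in the pregnancy-test row, at Visit 1. Section 9.3.1 on that visit: "The visit should take place maximal 8 months before the treatment start (Biopsy harvesting"). Section 7.1 excludes women who are pregnant or expect to become so within 24 months of surgery, and 8.6 advises contraception. Section 10.1.2 says that pregnant participants "will not be subjected to the dGEMRIC MRI due to the need to apply a contrast agent".

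**Renal function.** Section 9.3.6: "The renal function will be assessed before the contrast agent" is given. Section 9.3.7 repeats this, and the schedule marks GFR at Visits 6, 7 and 8.

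**The concern.** A safeguard against a contrast reaction, or against contrast in pregnancy, has to be in force when contrast is given. The protocol does this for renal function. For allergy, it names a visit at which no contrast is described. For pregnancy, it sets a bar at the contrast scans but schedules no ascertainment after screening.

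The allergy row also disagrees with the eligibility list. It plans medication for enrolled patients with known allergies, while 7.1 excludes any known allergies. The next row of the same table handles antibiotic allergy by exclusion. A site reading both sections cannot tell what is intended for a patient with, say, an unrelated known allergy. Asthma, which the row also names, appears in neither exclusion.

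What is at stake is participant safety at up to three scans per patient, and a protocol that sites can follow consistently. No efficacy result depends on it.

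**Working it through.** The plan gives no figure on this point to reproduce. The check sets each safeguard beside the contrast visits and then adds up the age of the pregnancy test.

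**Safeguard against visit**

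| Safeguard | Where the protocol places it | Contrast described there? |
|---|---|---|
| Renal function / GFR | Visits 6, 7, 8 (9.1, 9.3.6, 9.3.7) | Yes |
| Anti-allergy medication | Before the operation (Table 3.7.1) | No |
| Pregnancy test | Visit 1 (8.6, 9.1) | No |

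The operation is Day 0 and the first contrast scan is Day 90, so the allergy measure as written comes about 90 days before the first contrast dose. No section repeats it at Visits 6–8.

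**Age of the only scheduled pregnancy test at each contrast scan**

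Inputs:
- Visit 1 to harvest: 0 days (screening immediately before harvest, an assumption for the shortest case) to 240 days (9.1, 9.3.1).
- Harvest to implantation: 19 to 30 days (9.1).
- Scans at days 90, 360 and 720, with acceptable delays of 2, 6 and 8 weeks, that is 14, 42 and 56 days (9.1).

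Shortest = 0 + 19 + scan day. Longest = 240 + 30 + scan day + delay.

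| Scan | Shortest (days) | Longest (days) |
|---|---|---|
| Month 3 | 19 + 90 = 109 | 240 + 30 + 90 + 14 = 374 |
| Month 12 | 19 + 360 = 379 | 240 + 30 + 360 + 42 = 672 |
| Month 24 | 19 + 720 = 739 | 240 + 30 + 720 + 56 = 1046 |

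Sensitivity to the inputs:
- Section 9.3.1 counts the 8 months back from harvest. If the schedule's 240 days are counted from Day 0 instead, the longest values fall by 30 days, to 344, 642 and 1016.
- The heading of 9.3.3 puts harvest at Day −14 or −28, and the synopsis says 3–5 weeks (21–35 days). Either in place of 19–30 days moves the results by at most 5 days (19 − 14 = 5; 35 − 30 = 5).
- The 1-day tolerance at implantation is ignored.

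Under every reading, the test is more than three months old at the first contrast scan and about two years old or more at the last.

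**The case against.** The strongest reply is that the protocol has more protection than these two items suggest, and much of that reply stands. Patients sensitive to gadolinium are excluded, which is the direct control for a known contrast reaction. Women expecting pregnancy within 24 months of surgery are excluded, which covers the contrast period as far as intention goes. Contraception is advised. Renal function is checked at exactly the right visits. The protocol rates the allergy risk minor, and section 3.7 says patients are treated to hospital standards. Section 10.1.2 is a rule for handling pregnancy and does not promise detection by a scheduled test.

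Four stronger readings are tempting, and the documents do not support them:
- *That the contrast safeguards in general miss the contrast visits.* The renal check does not.
- *That 3 × 108 = 324 contrast doses go uncovered.* That is a ceiling on doses. The allergy measure concerns only patients with known allergies or asthma, and the pregnancy bar only those who could be pregnant. Drop-outs and patients never implanted lower the count further.
- *That a patient can be eligible under Table 3.7.1 and a major protocol deviator under SAP section 4.3.* The table is a risk assessment; only 7.1 sets eligibility. What remains is a conflict of wording.
- *That sites would operate or give contrast relying on the Visit 1 test.* The protocol does not say so.

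What the reply does not remove: the only stated contrast-allergy mitigation names a visit without contrast and a group that the eligibility list excludes, and the pregnancy bar has no scheduled ascertainment near any scan to which it applies. An exclusion based on what the patient expects at screening does not establish her status months or years later.

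**Conclusion.** The point holds for two safeguards, allergy medication and pregnancy testing, and not for the renal check. The allergy measure conflicts with the contrast schedule and with the exclusions in 7.1. The pregnancy test is not aligned with the bar in 10.1.2: it is about 109–374, 379–672 and 739–1046 days old at the three scans, with maxima 30 days lower if counted from Day 0. The number of patients affected is not given and cannot be derived from the documents, beyond being smaller than 108. There is no effect on the sample size, power or primary analysis.

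This rests on two assumptions: that contrast is given only where the protocol describes it, and that the schedule's footnotes, which are not in the text available for review, add no pregnancy test. The pregnancy-test row carries no footnote mark. The sponsor should correct this as a safety and consistency matter.

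**What to change.** Reconcile Table 3.7.1 with sections 7.1 (both the gadolinium and the general allergy exclusion), 8.6, 9.1, 9.3.6, 9.3.7 and 10.1.2:
- State in Table 3.7.1 which visits the contrast-allergy measure is meant for, so that it agrees with the visits where contrast is given. State also which enrolled patients it can apply to, given the exclusions in 7.1, and how asthma is treated.
- Make the timing of pregnancy ascertainment in 8.6 and 9.1 agree with the contrast bar in 10.1.2.

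Which clinical rule to adopt is for the sponsor and investigators. The cost is a short amendment and, depending on that decision, possibly a simple test at existing visits. It should not be assumed that samples already taken would serve: the laboratory-test row is marked only at Visits 1 and 3, and 9.3.6 does not say how renal function is measured.

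The synopsis planned the last 24-month visit for 10/2021. If follow-up is complete, what remains is to report what sites actually did about allergy cover and pregnancy status before each contrast scan.

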3.8 Justification of choice of study population

Patients between 18 - 65 years of age with one or two symptomatic full-thickness cartilage lesions from 2 cm² to 8 cm² (per lesion, however, not exceeding a total size of 8 cm² for all lesions) on the femoral condyle and/or trochlea and/or patella of the knee due to a traumatic injury will be enrolled in this trial. The patients cannot display signs of advanced osteoarthritis, since this would lead to an inhomogeneous patient group: several not yet fully understood factors influence the clinical outcome and would therefore render the clinical results difficult to interpret. The proposed inclusion and exclusion criteria however, will lead to a patient cohort conform with the clinical indications of the standard therapies.

Patients will be selected from those attending normal consultations in the 5 clinical centers.

Document:	Clinical Study Protocol
Version:	V07
Page number:	47 of 80
Acronym	Nose to Knee II

4. STUDY OBJECTIVES

4.1 Overall Objective

The study aims at the comparison of a therapy with a mature graft versus a therapy with an immature graft for the regeneration of articular cartilage lesions in the knee after injury. Two main innovations are introduced: 1) the use of autologous nasal chondrocytes (NC) as cell source superior to articular chondrocytes (AC) and 2) the delivery of a mature graft as opposed to an immature graft. Data will also be analyzed retrospectively to identify the possibility of treatment selection in relation to the time after the initial cartilage injury (acute vs chronic cartilage lesions as defined by onset of symptoms).

4.2 Primary Objective

This proposed phase II trial seeks to primarily define whether a mature graft will improve the clinical efficacy for the patient, leading to an increase of at least 10 points in the main primary outcome (self-assessed score KOOS) after 24 months as compared to the group receiving the immature graft. Comparison between groups will allow assessment of whether the mature graft is superior to the immature graft.

4.3 Secondary Objectives

The secondary objective is to assess the stability and integration of the graft with the adjacent tissues as well as the remodeling of the implanted graft towards native cartilage.

Furthermore another questionnaire (EQ-5d) and an additional time point (12 month) for the KOOS will allow the more detailed analysis of the clinical development of the patient's recovery and elucidate changes in the perceived quality of life before and after treatment.

Additionally the number of treatment failure at 24 months will be analyzed. Treatment failure is defined as objective pathological clinical findings by the investigator directly correlated with subjective patients complaints resulting in a deterioration of the subjective clinical outcome assessed by KOOS and the 5 KOOS subscores. In case of treatment failure, a root cause analysis will be performed. A clinical deterioration is defined as reduction in the KOOS score of > 10 compared to baseline. A non-responding to treatment is defined as improvement of < 10 in the KOOS score.

